ED trackboard to determine if any patients currently in the ED at UCSF have made at least 4 ED visits in the past 12 months to UCSF or a combination of UCSF, ZSFG, or other hospitals based on shared data in our emergency department information exchange platform. If an individual is determined to be eligible based on these criteria, the faculty or study staff will review the chart for the most recent lab results including liver function tests (AST, ALT), platelets, and urine or serum pregnancy tests and urine toxicology testing specifically the presence of opioids including fentanyl (see exclusion criteria for specific cut off values). They will also review the past medical history and allergies in the electronic medical record to determine if the patient has cirrhosis or a document allergy to naltrexone or inactive ingredients contained in naltrexone XR. When a patient is determined to meet criteria inclusion by electronic record review, a study staff member will discuss the case with the ED provider caring for the patient to confirm the patient is willing to be approached, is clinically sober, and medically stable. The ED provider will then introduce the patient to the research staff who will discuss the study with the patient. The research staff member will assess the patient's willingness to participate. If a patient expresses interest in participating the research staff member will confirm the accuracy of information obtained from the medical record review that pertains to inclusion and exclusion criteria. If no discrepancies are found the research team member describe the study in detail and will perform a capacity assessment using the University of California San Diego Brief Assessment of Capacity to Consent to Research (UBACC) if there are any concerns about the participant's capacity to consent, such as ongoing alcohol or drug intoxication or withdrawal.

Capacity Assessment:

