Patients identified as frequent ED users will undergo an alcohol use disorder screening conducted by the research case manager, PI, or research fellow using a validated screening tool, the Alcohol Use Disorder Identification Test (AUDIT) which constitutes the screening component of SBIRT. The AUDIT places patients into one of four categories: low risk, risky, harmful, and severe. Brief intervention and pharmacotherapy have previously been shown to be most effective in those with harmful or severe use disorders [12]. Patients found to have at least harmful alcohol use based on the screening will be offered enrollment (AUDIT score ≥ 8). Enrollees will have blood and urine samples collected to screen for active opiate use including fentanyl, platelet counts, pregnancy, or significant liver disease (see exclusion criteria below) if no results are available in EHR. With the exception of urine pregnancy screening these tests are done as part of the routine care of emergency department patients with alcohol use disorders who are interested in accessing treatment. The results will be used to confirm inclusion/exclusion criteria are met. Patients meeting all criteria will be enrolled into the study and will receive 380mg of extended-release naltrexone as an intramuscular injection in the ED.

Naltrexone training and administration:

Study staff will compose and send e-mail before the start of the study, with input from UCSF ED nursing leadership, to all ED RNs informing of the intent and responsibilities of the study. Subsequently, during RN sign out (twice daily at 7am and 7pm) study staff will remind ED RNs about the study protocol to ensure as much staff as possible is aware of RN involvement and responsibilities. The shift-change information session will be performed for a two week run in period to assure all RNs are oriented.

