Patients who miss scheduled follow up injection visits will be contacted and asked to reschedule their injection visit as soon as possible. If they are able to reschedule within 2 weeks then no changes to study procedure are necessary. If they are able to reschedule within 2-4 weeks then they will be asked if they have used any opiates (including fentanyl) in the past 7 days. If they have not used opiates in the past 7 days then they will resume treatment, provided they are not endorsing any signs or symptoms of liver injury. If they endorse signs or symptoms of liver injury they will undergo screening as outlined above. If they endorse using opiates then they will not be allowed to resume treatment through the study. If a patient is unable to reschedule a missed injection appointment within one month they will not be allowed to continue in the study. If a patient is unable to resume treatment through the study then they will be provided with alternative follow up options (see transition to ongoing care).

Participant Payment:

A 20-dollar gift card incentive will be used to encourage attendance at the 6 monthly follow up visits required for XR-Naltrexone injections. Gift cards will be given at each of the six visits. The total value of gift cards available to each participant during the study period is \$120.00. Gift cards will be issued for locations that do not sell alcohol (e.g. Starbucks coffee).

Study Subjects:

The target population is patients with frequent ED visits for alcohol related complaints who may benefit from ED-initiated XR-NTX. The accessible population is all people in the San Francisco Bay Area presenting to the ED with an alcohol related complaint. The study sample will be adult

patients presenting to the UCSF ED with active hazardous or high risk alcohol use and ≥ 4 ED visits in the past 12 months for alcohol related complaints.

Inclusion Criteria:

- Age ≥ 21
- AUDIT score ≥ 8
- Frequent emergency department visits, defined as: At least 3 emergency department visits for in the past 12 months, including the index visit.

Exclusion Criteria:

- Opioid use: currently receiving opioid analgesics, self-report of opioid use in past 7 days, current physiologic opioid dependence, patients in acute opioid withdrawal, urine toxicology screen positive for opiates including fentanyl
- History of hypersensitivity to naltrexone, polylactide-co-glycolide (PLG), carboxymethylcellulose, or any other components of the diluent

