XR-Naltrexone carries the risk of inducing opiate withdrawal in patients with opiate dependence. Urine drug screening and direct questioning about opiate usage will be used to exclude any patients with possible active opiate use disorders.

XR-Naltrexone is an mu-opioid receptor antagonist and thus may limit the analgesic efficacy of these medications should the patient require them for an unexpected acute medical or surgical condition. The antagonist effect can be overcome by increasing the dose of opioid analgesic. This confers a theoretical increased risk of respiratory depression. Participants will be provided with a medical bracelet and/or wallet card that carries relevant clinical information for providers as well as contact information for the PI and research team (see previous description under Index ED visit)

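### Screening results have no age limit, so an old negative pregnancy test or urine opioid/fentanyl screen can satisfy the laboratory check before the first XR-NTX injection

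*Combined protocol and SAP*

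**What the plan says.** In Section II, Determination of Eligibility, staff are to "review the chart for the most recent lab results". The list covers AST/ALT, platelets, pregnancy tests and urine toxicology for opioids including fentanyl. No maximum age is given for any of them.

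Under Enrollment, new samples are taken "if no results are available in EHR". The same paragraph states: "The results will be used to confirm inclusion/exclusion criteria are met". Patients who meet all criteria then receive the 380 mg injection in the ED. It also states: "With the exception of urine pregnancy screening these tests are done as part of the routine care of emergency department patients", with the qualification that this refers to patients with alcohol use disorder who want treatment.

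The Exclusion Criteria list pregnancy, with no test timing. The opioid exclusion covers current opioid analgesics, self-reported use in the past 7 days, current dependence, acute withdrawal and, as a separate item, "urine toxicology screen positive for opiates including fentanyl". In Section III, Risks and risk minimization strategy, the control for induced opioid withdrawal reads: "Urine drug screening and direct questioning about opiate usage will be used to exclude any patients with possible active opiate use disorders".

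**The concern.** Read literally, any result on file, whatever its age, removes the trigger for a new sample. A patient whose last pregnancy test or urine screen was negative months ago, and who has had neither since, passes the laboratory part of eligibility on that old result. These are the two screened conditions that an old result describes least well, because both can change within weeks.

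The first dose is a monthly extended-release injection and cannot be withdrawn once given. For opioids, the plan itself names precipitated withdrawal as the risk that the urine screen and the questioning together are meant to control. For pregnancy, the stake is that a patient who meets an exclusion is dosed; Section III describes no pregnancy-specific harm. Nothing here biases the analysis. The issue is participant safety and adherence to the plan's own exclusions.

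**Working it through.** The plan gives no figure on this point to reproduce. The check is to follow the eligibility rule through the text, and then to see how much opportunity there is for an old result to be on file.

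**Following the rule**

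1. *Chart review (Determination of Eligibility).* The latest result counts. If a test was done at the index visit, that result governs. If not, the latest result is an older one.
2. *Sample collection (Enrollment).* A sample is taken only when no result exists. An older result is a result, so no sample is taken.
3. *Use of the result (Enrollment).* It confirms the criteria and the injection follows. This is the final laboratory step and not merely a pre-screen.
4. *Any later rule requiring a same-visit test.* None was found in the Exclusion Criteria, Section III or Section V. The 7-day window in the opioid exclusion applies to self-report, not to the urine screen. Section III says urine screening will be used but not when. Section V has the study paying for urine drug and fentanyl screening as research-only procedures, again without timing.
5. *The missed-injection rule.* After a delay of 2–4 weeks, "If they have not used opiates in the past 7 days then they will resume treatment", provided there are no signs of liver injury. That rule applies to repeat doses in patients already screened and treated, so it does not cover the first dose. It does show that the plan regards opioid status as something to be asked about afresh.

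**What remains if the urine result is old**

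| Condition | Other checks in the plan | What could be missed |
|---|---|---|
| Opioid use | 7-day self-report, current analgesics, dependence, withdrawal, direct questioning | Undisclosed recent use without clinical signs |
| Pregnancy | General confirmation of chart information with the patient | Pregnancy that is unrecognised or not raised |

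Enrollment describes the sample as a screen for active opioid use, and Section III pairs the screen with questioning. An old screen cannot show current use, so in that case questioning and clinical signs carry the whole load.

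**Opportunity for an older result to exist**

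Earlier ED visits in the year = visits required (or observed) − 1 index visit.

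- Inclusion Criteria, "At least 3 emergency department visits for in the past 12 months, including the index visit": 3 − 1 = 2 at minimum.
- Determination of Eligibility, threshold of 4, assuming the index visit is counted: 4 − 1 = 3 at minimum.
- Sample Size, UCSF patients with at least 4 alcohol-related visits, median 6: 6 − 1 = 5.

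These are opportunities and not a risk estimate. The plan does not say which tests were done at those visits, and some may have been at other hospitals.

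**The case against.** The strongest reply is that the clause was meant only to avoid redrawing labs that the index visit has already produced. Enrollment speaks of active opioid use and calls most of the tests routine, which fits that reading. It may well be the intent, but the text does not say so. The routine-care statement leaves out pregnancy testing and is limited to patients seeking treatment, while Section V calls the urine drug and fentanyl screens research-only. A same-visit result therefore cannot be assumed.

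Second, an old negative does not clear a patient on its own. All criteria must be met, several of them describe current status, and staff confirm chart information with the patient. This stands, and it narrows the gap to undisclosed opioid use and unrecognised or unmentioned pregnancy. It does not close it: an old negative can be accurately recorded and still be out of date, and the check orders no test.

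Third, the visit counts say little. They are not counts of tests. The median of 6 comes from a more heavily attending group than the inclusion rule requires, and the shared ED platform is described as holding visit dates and diagnoses, not laboratory results. If pregnancy testing is not routine, an old pregnancy result is also less likely to be on file, in which case a new sample is required. All of this stands as a limit on size. It does not change what happens when an old result is on file.

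Finally, the same clause governs AST/ALT and platelets. Singling out two tests is a judgement about which results go out of date fastest, not something the documents establish.

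**Conclusion.** The concern holds. As written, the plan lets a pregnancy or opioid/fentanyl result of any age satisfy the laboratory check before the first injection when no newer result exists. The gap is widest for pregnancy and partly covered for opioids.

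The number of patients affected cannot be derived from the documents. The conclusion rests on a literal reading of the collection clause; if staff already test everyone at the index visit, the change only records that practice. It should be corrected because it concerns the safety of a first dose that cannot be reversed and the correction is cheap. It has no bearing on the study's estimates.

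**What to change.** For these two tests, replace the collection clause under Enrollment with wording such as:

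> A urine opioid/fentanyl screen and, where applicable, a urine or serum pregnancy test must be collected during the index visit (tests already done at that visit count) and resulted before injection. Earlier EHR results for these tests serve as a pre-screen only.

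Record in REDCap the date of each result relied on. The AST/ALT and platelet rule can stay as it is; a maximum age for those results would be a reasonable addition but is not needed for this point.

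The cost is one sentence, one date field per test, and one urine test (opioid/fentanyl) or two (with pregnancy, where applicable) per patient reaching this step, where not already done at that visit. For 25 enrollees that is at most 25 × 2 = 50 tests. Replacements and screen failures add to this, so the total is not fixed. Section V already has the study funding research-only urine drug and fentanyl screening. The real downside is waiting for results, which lengthens the ED stay, and total ED length of stay is one of the feasibility outcomes in Section IV.

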Screening, brief intervention, and referral to treatment (SBIRT) has demonstrated efficacy in reducing risky alcohol use and reducing net healthcare costs. SBIRT is strongly recommended for use in the emergency department by the CDC, the US Preventive Services Task Force, and the National Institute on Alcohol Abuse and Alcoholism [10]. Despite these recommendations, SBIRT is rarely utilized due to numerous barriers to implementation including time and cost [11]. Emergency department use of SBIRT paired with facilitated referrals where ED staff ensure eligibility, insurance clearance, and assist in scheduling and transportation to follow up visits has demonstrated feasibility and may reduce the barriers to accessing treatment [7].

Even though pharmacotherapy is recommended as the standard of care for alcohol dependence, fewer than 1 in 4 dependent patients receives treatment with an approved agent [6] and its use in EDs is virtually non-existent. Of the four drugs approved for treatment of alcohol dependence, extended release naltrexone (XR-NTX) has been found to be superior at reducing healthcare utilization, increasing detoxification facility use, and reducing total cost [5]. It may also be perceived by providers as a more feasible treatment to administer [6]. While there is a growing body of evidence supporting the efficacy of ED-initiated, medication-assisted treatment (MAT) of opiate use disorders [7], little research exists on ED-initiated MAT for alcohol use disorders. We propose to address this knowledge gap via a pilot study to examine the feasibility of ED-initiated XR-NTX paired with telemedicine SBIRT for frequent ED users with alcohol use disorders. Enrolled patients will receive up to 3 consecutive months of XR-NTX. A dedicated research case manager will be available for all participants. The research case manager will

outreach to the participants in the community to coordinate monthly injections. An addiction specialist from a community organization familiar the drug will administer the XR-NTX.

This study aims to address CARESTAR's Funding Priority to "support nonprofit health advocacy organizations, state and local agencies, providers of care and community partners in the development and implementation of meaningful, impactful and sustainable health related initiatives that improve care and expand access to emergency and trauma services, particularly with vulnerable populations."

II. Study Design and Procedures:

Overview of Design:

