The medical bracelet or wallet card will alert providers that opiate dosing adjustments may be necessary to adequately treat acute pain should the patient require treatment during the study period. It will provide information about the added precautions necessary should that patient require opioid pain management. Specifically, as the amount of opioid required to achieve adequate analgesia may be increased any resulting respiratory depression may be deeper and more prolonged. Therefore a fast acting agent is preferred and the amount of opioid analgesic should be titrated to the clinical effect in a setting equipped for cardiopulmonary resuscitation. The PI will be available by phone for emergency consultation at any time.

Visit 2-3 study procedures:

Patients will receive a monthly intramuscular injection of extended release naltrexone for up to 3 consecutive months during visits for which the research case manager will outreach to the participants in the community. Injections will be administered in an outpatient setting by an addiction community provider familiar with XR-Naltrexone, or in the UCSF ED depending on patient preference. A 20-dollar gift card incentive will be used to encourage follow-up at the time of each injection. We will follow participants for 12 months from the time of enrollment (an additional 9 months after the final dose of XR-NTX administered on behalf of the study). Specimens for alcohol biomarker testing will be collected at follow up visits.

At each of the monthly follow up visits we will collect data on a) feasibility measures and b) study outcomes. During the follow-up period, the research case manager will track all participants and we will continue to collect data on study outcomes using REDCap including ED and inpatient hospital use, substance use, readiness to change, and engagement in substance use recovery/rehabilitation via community treatment programs, as well as subsequent doses of XR-Naltrexone administered. This data will be collected by administering the same validated questionnaires used in the index visit (AUDIT, ASI, SIP-2R). The PI and research fellow will also query the EDIE system and UCSF EHR monthly in order to identify any emergency department visits that could be related to the study procedures.

Follow up procedures after visit 3:

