Following completion of the 3rd injection visit the patient will no longer receive XR-Naltrexone through the study. They will be encouraged to continue engaging with other community health providers to continue treatment, but are not required to do so. During the 9 months after the final injection visit the patient will contacted by phone approximately once a month by a member of the research team to collect outcome data as well as to discuss any ongoing treatment or changes in their health that occurred after the completion of the treatment period. At the end of the 12 month study period a data analyst will conduct a final review of the EHR and EDIE network to complete the collection of outcome data.

Case management services between study visits 1-3:

Between injection visits, the research case manager will be available to participants to assist with their needs including being connected to longer term case management services, connection with a primary care provider, or other services they may need related to food, clothing, and shelter. If participants who have chosen to follow up with community providers are having difficulty

making appointment, for example because they cannot find transportation, the research case manager can facilitate transportation to appointment. Participants can also choose to switch from following up in the UCSF ED to community providers of XR-NTX at any time. In such cases, the research case manager will coordinate referral to an alternative provider in San Francisco who can administer XR-NTX. Participants will be able to contact the study case manager by phone or meet in person depending on the case manager's availability.

Transition to ongoing care:

Patients who wishes to receive treatment with XR-Naltrexone after completing their 3 injections or after dropping out of the study will have the following options:

1. If the patient has been receiving injections during the study from a community provider they may continue treatment after the 3rd injection or choosing to drop out of the study.
2. If the patient has been receiving injections during the study in the UCSF ED they can be referred to a community site that administers XR-Naltrexone to establish treatment.

Handling of missed injection visits:

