The risk of bias is substantial given that all enrollees are to be treated with XR-NRT and the study is not randomized or blinded and the population of interest is at high risk of being lost to follow up. We intend to conduct both an intention to treat analysis and a per protocol analysis, though our sample size may limit the utility of this approach. We will employ an independent data analyst to collect the ED visit counts and perform the final statistical analysis.

Statistical issues:

Statistical Test: Paired T Test

Hypothesis:

ED initiated Treatment of alcohol use disorders with multi-modal therapy reduces alcohol related ED visits in patients with frequent ED visits for alcohol related complaints

Sample Size:

We will enroll 25 patients. As a feasibility study our sample size was chosen as it represents a reasonable patient load for a single case manager. Because this population is difficult to retain in treatment, we anticipate the drop-out rate will be significant. Patients who drop out of the study (either withdraw or are lost to follow up) will be replaced with new enrollees until 25 patients have been recruited into the study. The goal of this practice is to maximize the benefit to the patient population, avoid wasting donated study medication, and to allow the research team to optimize recruitment and retention strategies.

Last year 42 patients presented to the UCSF Emergency Department at least 4 times for an alcohol related complaint. Of this group the mean number of visits was 8.49 with a SD of 8.58. The median number of visits was 6. The number of visits ranged from 4-47. After excluding 2 outliers (40 and 47 visits, each $> 3SD$ above the mean) the mean was 6.78 visits with a SD of 3.5 visits.

We estimate a standardized effect size of 0.584 would represent 2-5 emergency visits for alcohol related complaints. This equates to a 29-59% reduction in ED utilization, which is clinically relevant.

Data management plan:

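### The follow-up gift card is tied to injection visits, so phone assessments and patients who stop injections have no stated incentive, and a truthful opioid answer may cost the card

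*Combined protocol and SAP*

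**What the plan says.** Two places set the payment, both in section II. Visit 2-3 study procedures says: "A 20-dollar gift card incentive will be used to encourage follow-up at the time of each injection". Participant Payment says: "A 20-dollar gift card incentive will be used to encourage attendance at the 6 monthly follow up visits required for XR-Naltrexone injections". It adds "Gift cards will be given at each of the six visits" and gives a total of 120 dollars per participant.

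The number of injections is lower than six. Section I says: "Enrolled patients will receive up to 3 consecutive months of XR-NTX". Visit 2-3 study procedures, Follow up procedures after visit 3, and section V all keep to three.

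After the third injection, Follow up procedures after visit 3 provides that for nine months "the patient will contacted by phone approximately once a month", to gather outcome data. It mentions no payment. The case manager is to track every participant and repeat the baseline questionnaires during follow-up. Biomarker specimens are taken at follow-up visits.

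Handling of missed injection visits adds an opioid question when a missed visit is rescheduled 2-4 weeks late. It then says: "If they endorse using opiates then they will not be allowed to resume treatment through the study".

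Section IV acknowledges that "the population of interest is at high risk of being lost to follow up" and plans both intention-to-treat and per-protocol analyses.

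**The concern.** A follow-up incentive should buy outcome data. As worded, this one accompanies the injection. A patient who stops injections early loses the remaining cards, and the only routine in-person visits described after the index visit are the injection visits. An intention-to-treat analysis needs data from exactly those patients. The phone phase, where most of the twelve months of patient-reported data would come from, has no stated incentive for anyone.

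The outcomes exposed are those that need the patient: drinks per week, heavy drinking days, AUDIT, SIP-2R, PEth and urine ethyl glucuronide. If patients who stop do less well and are seen less often, the before-after change in those who are seen will look too favourable.

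The second issue is the screening answer. At a visit 2-4 weeks late, the only opioid check stated is the patient's own report. If a yes also costs the card, payment works against the truthfulness of that report. The liver-symptom questions at later injection visits (section III) raise the same issue, because an injection can be withheld pending results.

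**Working it through.** **1. The plan's own figure.** Participant Payment: 6 visits × 20 dollars = 120 dollars. This reproduces the stated total.

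**2. The same rule on the three-injection schedule.**
- Card at all three injections, index included: 3 × 20 = 60 dollars.
- Card at visits 2 and 3 only: 2 × 20 = 40 dollars.
- Left over if 120 dollars stands: 120 − 60 = 60 dollars (3 cards), or 120 − 40 = 80 dollars (4 cards).

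Six paid injection visits and at most three injections cannot both be right.

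**3. Share of contacts with a stated incentive.** After the index visit there are 2 injection visits and about 9 phone contacts, 11 in all. Paid share: 2/11 = 18%. Counting the index visit as a paid contact: 3/12 = 25%. None of the roughly nine calls is paid.

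**4. Where payment differs by treatment status.** The calls are unpaid for completers and stoppers alike, so they create no payment difference between them. That difference can arise only at visits 2 and 3.

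**5. What an opioid report could cost.** At a late visit 2 the patient could lose the cards for visits 2 and 3: 2 × 20 = 40 dollars. At a late visit 3: 20 dollars. This holds only if the card requires an injection. The wording under Visit 2-3 study procedures points that way; Participant Payment speaks of "attendance at the 6 monthly follow up visits required for XR-Naltrexone injections", which leaves it open whether a patient who attends but is not injected is paid.

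**6. Are missing data mainly from stoppers?** The documents give no dropout or response rates, so this is illustration only. Let s be the fraction who stop, p_s the fraction of stoppers observed and p_c the fraction of continuers observed, with p_c assumed to be 0.8. The share of missing data that comes from stoppers is

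s(1 − p_s) / [s(1 − p_s) + (1 − s)(1 − p_c)]

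| s | p_s = 0.8 | p_s = 0.5 | p_s = 0.2 |
|---|---|---|---|
| 0.2 | 20% | 38% | 50% |
| 0.4 | 40% | 63% | 73% |
| 0.6 | 60% | 79% | 86% |

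For example, with s = 0.4 and p_s = 0.5: 0.20 / (0.20 + 0.12) = 0.63. Stoppers supply most of the missing data under some assumptions and not under others.

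**7. Which outcomes need contact.** The change in alcohol-related ED visits is taken from the electronic health record and the shared ED visit platform, with monthly queries and a final review by a data analyst. It needs no attendance. The questionnaires and drinking measures need a conversation; the two biomarkers need a specimen, which a phone call cannot provide.

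**The case against.** The strongest reply is that the primary outcome for statistical analysis is untouched, because ED visits are counted from records. That stands. A reader might infer that outcome data in general, or the intention-to-treat analysis of ED visits, will be lost through the payment rule. The documents do not support this.

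A reader might also infer that data will be missing mainly in those who stop treatment. This cannot be derived: no rates are given, and most contacts fall after study injections have ended for everyone. One could assume response rates and a smaller benefit in non-responders and compute a percentage overstatement, but that would measure non-response under any payment scheme, not the effect of this one.

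The opioid point is narrow. The question is tied to rescheduling at 2-4 weeks, the word for attendance may mean that an uninjected patient is still paid, and nothing shows that 20 to 40 dollars would lead patients to conceal use. The narrowness stands; so does the ambiguity, which is itself worth removing.

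The plan has other retention measures: study cell phones, transport help and tracking of all participants. Doses received and three-month retention are feasibility outcomes, so encouraging injection attendance fits the aims. The plan also says openly that its risk of bias is substantial. All this lowers the stakes but does not argue for tying payment to the injection.

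Finally, patients who cannot reschedule within a month leave the study, and dropouts are replaced. A payment change cannot recover data from patients so removed. That loss comes from those rules, not from the card.

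**Conclusion.** The point holds in a limited form. As worded, the card follows injection visits, and no payment is stated for about 9 of 11 contacts after the index visit or for patients who have stopped injections. That no such payment exists is read from silence; the consent form is not part of the public text and may say more.

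The consequence is a risk of more, and possibly treatment-related, missing data in the contact-based secondary outcomes. Its size is unknown. The payment difference between stoppers and continuers is limited to visits 2-3; the unpaid calls are a separate weakness in the same outcomes. The disincentive to report opioid use is confined to visits rescheduled 2-4 weeks late, is worth at most 40 dollars on the three-injection schedule, and depends on reading the card as requiring an injection.

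The contradiction between six paid injection visits and three injections is plain on the page. The remedy is cheap enough that the change should be made even though the bias cannot be sized.

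**What to change.** In Visit 2-3 study procedures, Participant Payment and the consent form:

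- Pay the card for attending and completing the outcome assessment, whether or not an injection is given and whatever the patient answers to the opioid or liver questions. Tell patients so.
- Keep this for patients who stop injections but remain in follow-up.
- Reconcile the six paid visits and 120 dollars with the limit of three injections stated elsewhere.
- If 120 dollars stands, use the three or four cards that injection visits do not need for selected phone assessments, including the last.

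Cards for calls would support the questionnaires and drinking measures, not the biomarkers.

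The cost is wording in two subsections and the consent form, slightly more cards spent, and sending the cards for phone contacts electronically or by mail. Spending stays within the stated total if that total is confirmed; otherwise the extra cards need a budget line. No treatment rule changes.
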